- Subset of preselected *T. cruzi* serology positive and Chagas endemic specimens with limited sample volume that have comparator and supplemental testing data from a previous clinical study. If any discrepant ABBOTT PRISM Chagas results occurs between new results and the previous clinical study results, all of the archived specimens in these 2 categories will be tested with the ABBOTT PRISM Chagas assay.

The Abbott monitor will provide specific details of which specimens do not require comparator testing. All comparator testing will be performed according to the manufacturer's instructions and will include retesting, where required.

The comparator assay results will be compared to the corresponding results of the investigational assay.

E. Supplemental Testing

HIV, HBV and HCV nucleic acid testing (NAT) results for each of the donor specimens will be provided to Abbott to further characterize the donor specimens.

Specimens from donors, individuals at increased risk, individuals from endemic areas, Recovered HBV Individuals (for HBsAg assay) and individuals with HTLV-I/II associated diseases that are repeatedly reactive by either the Alinity s investigational assay or the comparator method or repeatedly gray zone negative (≥ 0.80 S/CO to < 1.00 S/CO) by the Alinity s investigational assay will be further tested using FDA licensed assays or research use only methods. This supplemental testing will be performed at the clinical sites or at external reference laboratories. Results obtained from this testing will be used to better characterize the specimen and assess final status.

The detailed algorithms for supplemental testing will be provided in a separate document for use with the clinical study protocol. Supplemental testing will be performed per each assay algorithm and if a specific assay is no longer commercially available or changes occur in the donor center's routine procedure, a revised version of the algorithm will be provided by the clinical monitor. Additional testing may be performed based on the clinical site's internal supplemental testing procedures. Data generated will be provided to Abbott and will be used for informational purposes.

Preselected positive specimens for each assay will have documented positive results prior to testing at the clinical sites. Supplemental testing is not required, but may be requested by the monitor for troubleshooting purposes.

Confidential Information

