Specimens should be shipped to Abbott Laboratories for additional testing or to a reference laboratory for supplemental testing as directed by the Abbott monitor. Store the specimens at -20 °C or below and ship overnight on dry ice. When shipped, specimens must be packaged and labeled in compliance with

Confidential Information

This material is the property of Abbott Laboratories and must not be disclosed or used, except as authorized in writing by Abbott Laboratories.

applicable state, federal, and international regulations governing the transport of clinical specimens and infectious substances.

A specimen may be removed from the study if the sample is found unacceptable for testing (e.g. inappropriate handling prior to testing, inadequate volume), or for other assignable causes. The reason for removal must be documented on an Incident CRF. Specimens removed from the study may need to be replaced, if deemed necessary by the Abbott monitor, to meet requirements for the minimum number of specimens.

B. General Study Procedures

1. Assay and/or System Configuration

The investigational Alinity s software is installed onto the Alinity s System at the time of instrument installation. The monitor will provide instructions on software configurations needed to start the study.

2. Instrument System General Procedures

Maintenance procedures are to be performed as instructed in the Investigational Alinity s System Operations Manual. Reports for maintenance and any documentation for component replacements that occurred during the study should be filed in study records.

The on-board inventory of the Alinity s System supplies and reagents will be checked daily. Load consumables and update inventory as necessary.

Refer to the Investigational Alinity s System Operations Manual.

3. Assay Calibration

Each Alinity s blood screening assay will be calibrated as described in the Alinity s Assay Clinical Brochure and the Alinity s Calibrator Clinical Brochure. The calibrator lot number and expiration date information will be read from barcodes when the material is tested on the instrument system. Refer to Calibration Procedures Section of the Alinity s System Operations Manual.

Calibration is to be performed for each investigational reagent lot. Print or transfer electronic report of the calibration and control results for each reagent lot tested. Refer to the Alinity s Assay Clinical Brochure and Alinity s Calibrator Clinical Brochure for frequency of calibration.

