Donor specimens used in the study are collected as part of the routine blood donation process. Events related to the blood or plasma donation process will be handled according to the donor center procedures and not recorded in the study files.

For donor follow-up specimens collected under this protocol, subject adverse events will be documented if they occur. It is expected that drawing blood or plasma may cause pain, bruising, lightheadedness, and on rare occasion, infection

Confidential Information

This material is the property of Abbott Laboratories and must not be disclosed or used, except as authorized in writing by Abbott Laboratories.

Page 23 of 34

at the site of the blood draw. These events will not be recorded as adverse events as they are considered to be normal events that may occur during the course of a blood or plasma draw. Other events that may occur such as fainting, that are not routinely associated with a blood or plasma draw, must be recorded on the Subject Adverse Event Case Report Form and be followed to satisfactory resolution.

A **Subject Adverse Event** is any unfavorable or undesirable medical occurrence (e.g., sign, symptom, or disease) temporally associated with the specimen collection procedure performed.

A **Subject Serious Adverse Event** is an untoward medical occurrence that:

- results in death
- is life-threatening
- requires inpatient hospitalization or prolongation of existing hospitalization
- results in persistent or significant disability/incapacity, or
- results in a congenital anomaly/birth defect.

IX. Statistical Procedures

A. General Information

All data analyses will be performed, and tables and listings of data will be provided by ADD Statistics using SAS version 9.2 or higher.

If revised or additional analyses are required, a description of the additional or revised analyses and justifications for the changes will be documented and approved by the same functional areas as the original approvers to the protocol.

The Abbott monitor will review all test results and may request that certain observations be excluded from analysis if there is an assignable cause, i.e., control or validity criteria failure, instrument errors or problems, acknowledged technologist error, and/or noncompliance with the study protocol. All results tested according to the protocol and not excluded will be eligible for analysis.

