The statistical analysis output along with a listing containing each observation collected for this study will be completed. The listing will be printed for data included in the analysis and excluded from the analysis. The excluded listing will include the reasons for exclusion. A summary of the usage of every test result will also be completed, together with the final analysis results, to ensure that there is no data point missing or misplaced in the analysis.

There is no plan to perform interim analyses that evaluate interim data against acceptance criteria. However, interim data monitoring will be conducted to ensure data meets validity criteria and minimum sample size requirements.

B. Statistical Analysis Description

Confidential Information

This material is the property of Abbott Laboratories and must not be disclosed or used, except as authorized in writing by Abbott Laboratories.

Page 24 of 34

1. Reproducibility

a. Study Design

Assay reproducibility will be determined by testing controls and members of a panel at a minimum of three sites with one instrument using a minimum of 3 lots of each Alinity s blood screening assay reagents, calibrators, and controls.

b. Analysis Variables

The analysis variable is Alinity s assay S/CO values for all panel members and controls.

c. Statistical Analysis Method

The analysis method is based on CLSI EP15-A2E. The reproducibility panel members and the Negative and Positive controls will be tested twice a day for a minimum of 5 days per reagent lot (minimum 3 lots) and site (minimum 3 sites). Within each run, each panel member/control will be tested in two aliquots and two replicates will be assayed per aliquot, resulting in four results per sample.

Overall Analysis

Data from all sites and reagent lots for each reproducibility panel/control member will be used for the reproducibility analysis. The following individual variance components will be estimated: within-run, between-run, between-day, between-lot, between-site, and lot-site interaction. The within-laboratory variance is defined as the summation of within-run, between-run, and between-day variance components. The overall assay variability is defined as the summation of within-run, between-run, between-day, between-lot, between-site, and lot-site interaction variance components. The estimates of the mean S/CO, standard deviation (SD) and %CV will be calculated.

By Site Analysis

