A similar analysis as overall analysis will be performed by site for each reproducibility panel/control member. The within-run, between-run, between-day, and between-lot variance components will be estimated. The within-laboratory variance is defined as the summation of within-run, between-run, and between-day variance components.

By Lot Analysis

A similar analysis as overall analysis will be performed by reagent lot for each reproducibility panel/control member. The within-run, between-run, between-day, and between-site variance components will be estimated.

Confidential Information

This material is the property of Abbott Laboratories and must not be disclosed or used, except as authorized in writing by Abbott Laboratories.

Page 25 of 34

The within- laboratory variance is defined as the summation of within-run, between-run, and between-day variance components.

Percent Agreement

A percent agreement and the 95% confidence interval with the expected results from a sample (reactive or nonreactive) will be performed for each panel/control.

d. Sample Size

The design of the study is based on CLSI EP15-A2E. Each reproducibility panel/control member (sample) will be tested twice a day for 5 days in replicates of 4 at a minimum of 3 sites, using a minimum of three (3) reagent lots to obtain about 360 replicates for each sample (i.e., 2 runs/day x 5 days x 4 replicates x 3 sites x 3 lots = 360 total replicates).

e. Level of Significance/Confidence Statement

A 95% confidence interval will be constructed for agreement analysis.

f. Data Handling Convention

All results from this testing that are performed according to the protocol and not excluded will be eligible for analysis. Reasons for any exclusion will be captured in the database.

g. Outlier Detection

The range of data (difference between the maximum and minimum within a run) will be calculated by sample, site, lot, day, and run. If the range of the data is greater than 9 times the standard deviation (SD) using the applicable imprecision product requirement, investigate and identify the run as an outlier run and the run will be repeated for that panel/control. If the $(5.5 \times SD) < (\text{range of the data}) \leq (9 \times SD)$ from the applicable imprecision product requirement, investigate and identify the run as an outlier run but do not repeat the run for that panel/control.

The reproducibility analyses will be performed with the outlier(s) included and with the outlier(s) excluded.

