Sensitivity can be also calculated as the proportion of repeatedly reactive (RR) specimens with positive status from specimens with positive status and nonreactive (NR) specimens with indeterminate status:

$$\text{Sensitivity} = A / (A + D + E) \times 100\%$$

A two-sided 95% confidence interval for overall sensitivity will be calculated using the exact method based on the binomial distributions.

All sensitivity calculations described above will also be done for the comparator assay.

d. Sample Size

Sample size for specificity is maximum of 15,000 and calculated based on the minimum power of 80% and $\alpha \leq 0.05$.

Sample size for sensitivity is not determined using statistical power calculations. Sample size is determined by the number of available specimens.

e. Level of Significance/Confidence Statement

Two-sided 95% confidence interval (CI) will be provided.

Confidential Information

This material is the property of Abbott Laboratories and must not be disclosed or used, except as authorized in writing by Abbott Laboratories.

f. Data Handling Convention

All results from this testing that are performed according to the protocol and not excluded will be eligible for analysis. Reasons for any exclusion will be captured in the database.

X. Conduct of the Study

A. Responsibilities for Conduct of the Study

- 1) The investigator will have written and dated approval/favorable opinion from the [Institutional Review Board (IRB) or Independent Ethics Committee (IEC)] for the protocol and other documents as specified by the [IRB/IEC] before initiating the study. In some cases, the [IRB/IEC] may provide an expedited or exception review.
- 2) The investigator is responsible for reporting to the [IRB/IEC] and obtaining the necessary approvals from his/her site administration.
- 3) Abbott Laboratories will not initiate the study until the required pre-study documents are received from the site. Pre-study documents are aligned with GCP requirements and a detailed listing of the required pre-study documents will be provided to the investigator by the Abbott monitor.
- 4) The investigator will perform the study in accordance with GCP. The Abbott monitor will provide the investigator with the GCP-aligned list of investigator requirements.
- 5) The Abbott monitor will provide the investigator with the Guidance for Industry Investigator Responsibilities – Protecting the Rights, Safety, and Welfare of Study Subjects (October 2009) for reference.

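### Clinical specimen results may be excluded after the sponsor's monitor has seen them, and no specificity or sensitivity estimate that includes the excluded results is planned

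*Combined protocol and SAP*

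**What the plan says.** Section IX.A gives the exclusion rule for the whole study: "The Abbott monitor will review all test results and may request that certain observations be excluded from analysis if there is an assignable cause". It names the causes as "control or validity criteria failure, instrument errors or problems, acknowledged technologist error, and/or noncompliance with the study protocol".

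Section VI.A.3 (Specimen Handling, Storage, and Accountability) adds a second route: "A specimen may be removed from the study if the sample is found unacceptable for testing", "or for other assignable causes". That route needs an Incident CRF, and the monitor decides whether a removed specimen must be replaced.

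On traceability, Section IX.A provides for listings of included and excluded data and a summary of how every test result was used. It also says: "The excluded listing will include the reasons for exclusion".

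For the clinical specimens, Section IX.B.2.f says: "All results from this testing that are performed according to the protocol and not excluded will be eligible for analysis". Nothing in IX.B.2 describes an analysis that puts excluded results back.

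Section III.B (Ethics) states blinding to specimen category for the testing sites only. Under Section III.A the monitor designates the specimens for each assay study.

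For preselected positives, Section III.E says: "Supplemental testing is not required, but may be requested by the monitor for troubleshooting purposes".

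**The concern.** The person who asks for exclusions has already reviewed the results. Minor departures from the protocol, such as an extra freeze-thaw or a late re-centrifugation, can affect concordant and discordant specimens alike, but a discordant result is the natural reason to go looking for one. If a genuine cause is acted on mainly where the result was unfavourable, the estimate is biased upward even though each exclusion can be justified on its own. A listing shows what was removed. It does not show how many concordant specimens shared the same cause and stayed in.

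The quantities at stake are the donor specificity and the sensitivity in the positive panels. Both are close to 100%, so each rests on a handful of discordant specimens.

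**Working it through.** **Inputs from the documents.** Specificity is F/(C + F) and sensitivity is A/(A + D), with exact two-sided 95% binomial intervals (IX.B.2.c). There are 15,000 donors per assay; for three assays, 3,000 of these are plasmapheresis donors (VI.A.2). Preselected positive groups run from 50 (HIV-1 antigen positive/viral isolates) to 1,000 (HIV-1), with HIV-2 at 200 and *T. cruzi* parasite positive at 100 (VI.A.1).

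**Assumed, because the documents give no counts.** 15 false reactives in 15,000; 3 in 3,000; one miss per sensitivity group; and the number removed. All donors are treated as having negative final status.

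**Plan's own figure.** IX.B.2.d gives 15,000 for specificity with at least 80% power and alpha of at most 0.05. It states no null or alternative specificity, so the figure cannot be reproduced. It is not in dispute here. No acceptance limit is stated either, so whether an exclusion could turn a fail into a pass cannot be calculated.

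**Specificity.** Removing r false reactives leaves F unchanged and lowers C by r.

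| Donors, false reactives | Removed | Calculation | Specificity % (95% CI) |
|---|---|---|---|
| 15,000, 15 | 0 | 14,985/15,000 | 99.900 (99.835 to 99.944) |
| 15,000, 15 | 3 | 14,985/14,997 | 99.920 (99.860 to 99.959) |
| 15,000, 15 | 5 | 14,985/14,995 | 99.933 (99.877 to 99.968) |
| 3,000, 3 | 0 | 2,997/3,000 | 99.900 (99.708 to 99.979) |
| 3,000, 3 | 3 | 2,997/2,997 | 100 (99.877 to 100) |

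Each removal from 15,000 is worth about 1/15,000 = 0.007 points, and from 3,000 about 1/3,000 = 0.033 points. Removing 5 of 15 moves specificity by 0.033 points, while the observed false-reactive rate falls by a third.

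**Sensitivity.** Removing the only miss takes D from 1 to 0.

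| n | Miss kept: % (95% CI) | Miss removed: % (95% CI) | Rise in estimate (points) |
|---|---|---|---|
| 50 | 49/50 = 98.0 (89.4 to 99.9) | 49/49 = 100 (92.7 to 100) | 2.0 |
| 100 | 99/100 = 99.0 (94.6 to 99.97) | 99/99 = 100 (96.3 to 100) | 1.0 |
| 200 | 199/200 = 99.5 (97.2 to 99.99) | 199/199 = 100 (98.2 to 100) | 0.5 |
| 400 | 399/400 = 99.75 (98.6 to 99.99) | 399/399 = 100 (99.1 to 100) | 0.25 |
| 1,000 | 999/1,000 = 99.9 (99.4 to 99.997) | 999/999 = 100 (99.6 to 100) | 0.1 |

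The lower limit rises by 92.7 − 89.4, about 3.4 points before rounding, at n = 50, and by 98.2 − 97.2, about 0.9 before rounding, at n = 200.

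**Pooled check.** The three preselected HIV groups total 1,000 + 200 + 50 = 1,250. One miss gives 1,249/1,250 = 99.92% (99.56 to 99.998). With it removed, 1,249/1,249 = 100% (99.71 to 100), a rise of 0.08 points.

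**The case against.** The plan has real safeguards. An assignable cause is required, and IX.A gives its causes as a closed list, although VI.A.3 is looser. The monitor may only request an exclusion. Removal of a specimen needs an Incident CRF. Section VI.B.6 already looks beyond the single specimen when a control failure stays unresolved, because results since the last acceptable control run must then be evaluated. With the listings in hand, a reader could largely rebuild the all-results estimate. All of this stands and makes the gap narrower. What it leaves open is that no such estimate is committed to, and that noncompliance need not be applied evenly.

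The size is also modest. The interval in IX.B.2.c is for overall sensitivity, where one HIV miss is worth about 0.08 points. Many control, validity or instrument failures leave no usable result to put back.

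Three stronger readings are tempting, and the documents do not support them.

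- A reader might infer that reproducibility already receives the analysis missing here, since IX.B.1.g says: "The reproducibility analyses will be performed with the outlier(s) included and with the outlier(s) excluded". That covers runs flagged by a range criterion. For assignable-cause exclusions, IX.B.1.f is worded the same as IX.B.2.f, and neither adds a second analysis.
- A reader might infer that missed preselected positives will be retested out of the denominator. Section III.E requires their positive results to be documented beforehand, does not mention misses, and limits extra tests to troubleshooting. It does not say that such tests change final status, nor that they cannot. The detailed algorithms are in a separate document.
- A reader might infer that the monitor must be blinded. Blinding would help, but the monitor also directs supplemental testing and follow-up, so it would probably need a separate reviewer. It is not needed to close this gap.

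**Conclusion.** The point holds as a modest, inexpensive improvement. Exclusions can be requested with results in view, for causes as broad as any protocol noncompliance, with no even-application rule and no planned estimate that includes what was excluded. Both measures could be biased upward. On the assumed counts this amounts to hundredths of a point for combined specificity and 0.5 to 2.0 points for one miss in a sensitivity group of 50 to 200. It matters mainly in those small groups, where one decision separates a reported miss from 100%.

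The sizes rest on assumed numbers of discordant and removed specimens. The documents do not show that selective exclusion is intended or likely, and without an acceptance limit no changed conclusion can be demonstrated.

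**What to change.** In IX.A and IX.B.2.f:

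1. State that each assignable cause is applied to every specimen in the affected run, lot or handling event, whatever its result.
2. Report specificity and sensitivity a second time, next to the main estimates, including all excluded specimens that have a valid test result. In practice these will mainly be protocol-noncompliance exclusions.
3. Add one clarifying sentence: troubleshooting tests on preselected positives are listed but change neither their final status nor the denominator.

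Items 1 and 2 do different work. Even application removes the selection by result, but it can still take out a true miss. The second estimate keeps that miss visible.

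The cost is some wording, identifying the specimens that share each cause, and one repeat analysis. No new specimens are needed. The downside is a second figure that may be slightly less favourable.

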Refer to the Alinity s Assay Control Clinical Brochure to determine acceptability of the quality control results used during calibration. If unexpected results are obtained or problems are encountered, contact the Abbott monitor.

Confidential Information

This material is the property of Abbott Laboratories and must not be disclosed or used, except as authorized in writing by Abbott Laboratories.

Page 16 of 34

4. Assay Training

The study staff will be trained in the operation of the Alinity s System prior to performing protocol directed activities. This training will involve an overview of the system operation including system configuration, system maintenance, system calibration, control and specimen testing procedures.

Training materials (e.g., training panel) will be used to assess proficiency of the user performing the investigational assays. Assay training is to be performed by each user for each assay. Testing will be performed as described in a separate workflow document. The Abbott monitor will evaluate the results for acceptability.

5. Quality Control Validity Criteria

Daily quality control for each Alinity s blood screening assay will include all Alinity s assay controls tested a minimum of once each day, on each reagent lot tested for that day.

Refer to the Investigational Alinity s System Operations Manual for testing of the quality controls.

Daily quality control for each Alinity s blood screening assay will be assessed for validity using the ranges described in the Alinity s assay control clinical brochure.

6. Troubleshooting Quality Controls

The following steps must be used when troubleshooting and documenting quality control failures.

- 1) Determine if an assignable cause can be found (e.g., incorrect placement, bubbles). If an assignable cause can be found, correct the identified problem.
- 2) Retest the quality control from the **original control bottle**. If the quality controls are within the validity criteria, testing may continue.
- 3) If the quality control value still does not meet the validity criteria, test the quality control substituting a **new control bottle**. If the quality control value is within the established range, continue testing.
- 4) If the quality control value still does not meet the validity criteria, **repeat assay calibration** on the instrument and **repeat all quality controls**. If the quality control values are within the established range, continue testing.

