This material is the property of Abbott Laboratories and must not be disclosed or used, except as authorized in writing by Abbott Laboratories.

Page 18 of 34

C. Testing Procedures

All clinical laboratory site testing is to be performed according to the clinical protocol and the appropriate sections of the clinical brochures.

1. System Reproducibility

Alinity s System reproducibility testing will be performed at a minimum of 3 clinical sites using a minimum of 3 lots of each Alinity s blood screening assay reagents, calibrators, and controls.

Testing will include two runs per day on each of 5 (nonconsecutive) days with a minimum of one break of 1 day with a minimum of 3 Alinity s reagent lots at a minimum of 3 sites. Each reproducibility run will include four replicates tested for each reproducibility panel member.

Procedure

- 1) Test each Alinity s blood screening assay control (Negative and Positive plus any additional controls required for HIV or HTLV testing), if daily quality controls have not been already tested and assessed for validity.
- 2) Refer to the “Specimen Collection and Preparation for Analysis” section of the assay clinical brochure for detailed procedures on handling of samples prior to placing the reproducibility panel members on the Alinity s System.
- 3) Place the barcoded sample tubes in a sample rack as directed by the Abbott monitor.
- 4) Schedule an Alinity s release control for each assay. If release control is not already on the system, place the calibrator and control rack on the Alinity s System in the priority bay to schedule testing.
- 5) Testing as described in Steps 1 through 4 will be performed on each of five days for each reagent lot for each assay.

Note: If an error occurs during reproducibility testing, contact the Abbott monitor. The reproducibility testing for that day may need to be repeated. Errors which occur during reproducibility testing should be documented on an Incident CRF.

2. Specimen Testing

Testing will be performed to determine the agreement of specimen results obtained from each Alinity s blood screening assay to the comparator method.

Confidential Information

This material is the property of Abbott Laboratories and must not be disclosed or used, except as authorized in writing by Abbott Laboratories.

Page 19 of 34

Testing of the comparator method will be performed according to each comparator package insert.

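### Does the Section VI.C.1 site procedure leave the controls short of the 360 results each that Section IX.B.1 counts on?

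*Combined protocol and SAP*

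**What the plan says.** Section IX.B.1.c (Statistical Analysis Method) includes the controls by name: "the Negative and Positive controls will be tested twice a day for a minimum of 5 days per reagent lot", at each of at least three sites. It sets the within-run layout for both kinds of sample: "each panel member/control will be tested in two aliquots and two replicates will be assayed per aliquot, resulting in four results per sample". Section IX.B.1.d repeats this as the sample size: "Each reproducibility panel/control member (sample) will be tested twice a day for 5 days in replicates of 4 at a minimum of 3 sites". The variance components and percent agreement cover controls as well as panel members. So does the outlier rule in Section IX.B.1.g: "The range of data (difference between the maximum and minimum within a run) will be calculated by sample, site, lot, day, and run".

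The bench procedure in Section VI.C.1 is shorter. On replication it says "Each reproducibility run will include four replicates tested for each reproducibility panel member" and does not mention controls there. Procedure step 1 has each assay control tested "if daily quality controls have not been already tested and assessed for validity". Step 5 sets the repetition: "Testing as described in Steps 1 through 4 will be performed on each of five days for each reagent lot for each assay". The QC rule in Section VI.B.5 asks for "all Alinity s assay controls tested a minimum of once each day, on each reagent lot tested for that day".

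**The concern.** An operator working only from the numbered steps of Section VI.C.1 finds no instruction to load the controls as samples, in aliquots or in replicate. Step 1 falls away once daily QC has been done, so the second run of a day need contain no control. The release control in step 4 is scheduled separately and does not fill the gap. On that reading a site could complete Section VI.C.1 with one result per control per day per lot, while Section IX.B.1 expects eight (2 runs x 4 replicates).

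The main loss would be estimability. With one result per day, within-run and between-run variance cannot be separated from between-day variance, and a within-run range cannot be formed from a single value. The interval for control percent agreement would also be wider than the design implies.

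**Working it through.** **Inputs.** Two runs a day, 5 days, 4 replicates (2 aliquots x 2), 3 sites and 3 lots, from Sections IX.B.1.c and IX.B.1.d. The QC minimum is one result per control per day per lot, from Section VI.B.5.

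**The plan's figure.** 2 x 5 x 4 x 3 x 3 = 360. The aliquot form, 2 x 5 x (2 x 2) x 3 x 3, also gives 360. The figure reproduces.

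**The QC-only floor.** 1 x 5 x 3 x 3 = 45 per control, and 45/360 = 12.5%.

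**Degrees of freedom**, with 9 site-lot cells and days nested in each cell:

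| Component | 360 results | 45 results |
|---|---|---|
| Within-run | 9 x 5 x 2 x (4 - 1) = 270 | 0 |
| Between-run | 9 x 5 x (2 - 1) = 45 | 0 |
| Between-day | 9 x (5 - 1) = 36 | 36, with run and within-run variation mixed in |

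The plan does not say whether the lots at a site share the same five days. If they do, day within site has 3 x (5 - 1) = 12 degrees of freedom. The two zeros at 45 results do not change.

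**Percent agreement.** Section IX.B.1 does not name the interval method, so exact binomial limits and independent results are assumed. With full agreement the two-sided 95% lower limit is 0.025^(1/n):

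- n = 360: 98.98%
- n = 45: 92.13%

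With one discordant result it is the 2.5% point of a beta(n - 1, 2) distribution: 98.46% at 360 and 88.23% at 45.

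**Does the plan prescribe 45?** Four points from the text bear on this.

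1. Section IX.B.1.c is worded as a testing instruction for the controls, with frequency and replication. The opening of Section VI.C requires site testing to follow the clinical protocol, and Section IX is part of it.
2. Step 1 of Section VI.C.1 is a validity check before testing. Nearly the same step opens the specimen-testing procedure in Section VI.C.2, where no control reproducibility is estimated. It does not set a reproducibility count.
3. Where daily QC is already done, step 1 requires no control result inside the reproducibility run. Reaching even 45 therefore means treating routine QC as reproducibility data, which no section directs.
4. Section VI.C.1 also leaves out the two-aliquot layout for panel members. That detail appears only in Section IX.B.1.c, so the later section already supplements the procedure, and the controls can be read the same way.

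Taken together, the documents give one count for the controls, 360, and one section that does not repeat it.

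**The case for a change.** The strongest reply is practical: people at the bench follow the numbered steps, and nothing in those steps yields 360 control results or flags a shortfall. If QC results were then used in place of the missing data, they would carry a selection problem. Section VI.B.6 has a failed control retested until it is in range, and Section IX.A lets the monitor request exclusion for control failure. Dropping the failing results would understate control variability.

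Part of this stands. Section VI.C.1 is less complete than Section IX.B.1, and a cross-reference would make it easier to follow. The selection problem is also real, but only if QC data were substituted, which the plan does not propose.

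The rest does not carry. A site that produced 45 results per control would be departing from Section IX.B.1, and Section X.D defines a deviation against the whole protocol. Step 3 of Section VI.C.1 has sample tubes racked as the monitor directs, so the monitor can have controls loaded as samples. Section IX.A commits to interim monitoring against minimum sample size requirements, and Section III.C has the monitor review data and case report forms for compliance. A shortfall from 360 to 45 should show early. Whether sites also receive loading instructions in the clinical brochures cannot be judged from these documents.

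**Conclusion.** The concern does not call for a change. Section VI.C.1 is silent on control replicates. It does not state a different number, and Section IX.B.1 supplies the missing detail in plain terms. The 360 is arithmetically right and applies to controls as written.

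The 45 is a hypothetical floor. It needs a site to disregard Section IX.B.1, the monitor to miss the shortfall, and analysts to use routine QC as the reproducibility data. Only then would the within-run and between-run components be lost and the full-agreement lower limit fall from 98.98% to 92.13%. Those limits rest on the exact method and independent results. Section IX.B.1 sets no acceptance limit for control agreement, so the wider interval would not alter any decision stated there.

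There is no reason to withdraw or reduce the planned control analyses. A line in Section VI.C.1 pointing to Section IX.B.1.c would be good housekeeping, but it would change neither the design, the sample size nor the analysis.
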